16.2.6 Time to response in TILs

The analysis of time to response will consist of Kaplan-Meier estimates. The time to response data will be censored on those who do not respond at their last follow-up. The median time and 95% confidence interval will be presented.

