9.4.1.2 Clinical Management of TILs and TNILs

Along with assessing the overall tumor response (see Section 9.4.1.1, Tumor Response), each individual lesion will be assessed to determine appropriate clinical management. The RECIST 1.1 (Appendix B) response criteria will also be used to evaluate each individual tumor response.

Individual Lesion Complete Response (IL-CR): Complete disappearance of target lesion (whether measurable or not, and no new lesion(s) at the site of the target lesion) confirmation by an assessment 8 weeks after the end of the injections (Visit 6).

Individual Lesion Partial Response (IL-PR): Decrease in tumor burden $\ge 30\%$ relative to baseline confirmed by an assessment 8 weeks after the end of the injections (Visit 6).

Individual Lesion Progressive Disease (IL-PD): Progression is defined as >20% increase of at least 5 mm in the sum of the longest diameters of the target lesions or increase in tumor burden $\ge 20\%$ relative to nadir (minimum recorded tumor burden) or the appearance of one or more new lesions confirmed by an assessment 8 weeks after the end of the injections (Visit 6).

 Individual Lesion Rapid PD (IL-RPD): Is defined as an increase of >50% in tumor burden for lesions >2 cm in diameter or 100% tumor burden increase for lesion ≤2cm between visits.

Individual Lesion Stable Disease (IL-SD): Not meeting criteria for CR or PR, in

absence of PD (Decrease of tumor size <30% to increase in size <20% of less than 5 mm in the sum of the longest diameters of the target lesions).

	Individual Lesion	Individual	Progressive Disease	Stable Disease
	Complete Response	Lesion Partial	(PD)	(SD)
	(IL-CR)	Response (IL-		
	IL-CR to be	PR)		
	determined at the latest by Visit 6 (8	 IL-PR will be followed and assessed at 	 If IL-PD confirmed in two consecutive visits OR at Visit 6 (8 week 	 IL-SD will be followed and assessed up to
	week follow up), and will be followed for 6	assessed at Visit 6 (8 week follow up)	OR at Visit 6 (8 week follow up), TIL will be withdrawn and	assessed up to Visit 6 (8 week follow up)
	months • No additional	 If IL-SD is documented at 	alternative therapeutic intervention given	 Alternative therapeutic

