	 injections will be given to TILs who have achieved IL-CR prior to the 4th injection visit If recurrent at any 	Visit 6 or beyond, alternative therapeutic intervention will be offered	 If subject has additional TILs, will continue study participation If subject has only one, subject will be 	intervention will be offered if no IL-CR or IL-PR is observed by Visit 6.
TILs	point after IL-CR has been documented, then alternative therapeutic intervention offered (surgical excision, radiation, intralesional therapy etc.) based on patient preference	• If IL-PR continues, TIL will be closely followed until Visit 8, where alternative therapeutic intervention will then be offered	 withdrawn If IL-RPD occurs, treatment will be deferred that visit and will be reevaluated next visit. o If IL-PD confirmed, lesion withdrawn from study and alternative 	
			therapeutic intervention ○ If subject has more than one TIL, then lesions will continue to be a part of the study	
TNILs	 IL-CR to be determined at the latest by Visit 6 (8 week follow up), and will be followed for 6 	• IL-PR will be followed and assessed up to Visit 6 (8 week follow up)	 IL-PD at Visit 3 will undergo alternative therapeutic intervention 	 IL-SD will be followed and assessed up to Visit 6 (8 week follow up)
	monthsIf recurrent at any	 Alternative therapeutic 		 Alternative therapeutic

Table 7. Management of individual TILs and TNILs

point after IL-CR ha	s intervention will	intervention will
been documented a	It be offered if no	be offered if no
Visit 6, then	IL-CR is	IL-CR is
alternative	observed by	observed by
therapeutic	Visit 6	Visit 6
intervention offered		

9.4.2 High Resolution Ultrasonography of Squamous Cell Cancer:

The subjects will complete ultrasound assessments of their lesions at screening Visit (0), and at Visit 6 (second follow up visit).

METHOD:

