11.4 Process to implement study closure when significant risks or benefits are identified

The PI will be advised of all study related AEs and will determine if the study at a certain point may need to be closed due the AEs.

Study stopping criteria will include the following:

- Death within 30 days after the investigational treatment at least possibly related to the study treatment.
- Any herpetic event or complication requiring hospitalization that is at least possibly related to the investigational agent within 30 days to treatment.

Individual treatment stopping criteria will include the following:

- 75% or greater number of TILs meeting criteria for withdrawal.
- Identification of high-risk feature in one or more TILs during study participation.
- Persistent discomfort (consecutive weeks of lesion pain, burning, or itching of Grade 2 or more).

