16.1.2 Secondary Endpoints

 To assess the safety and adverse effect profile of talimogene laherparepvec in low risk cSCC. Adverse events to be assessed according to National Cancer Institute Common Terminology. This will be determined by incidence of all adverse events (AEs), grade ≥ 3 AEs, safety adverse events (SAEs), and events requiring the discontinuation of study drug, local effects on the tumor (ie, pain, inflammation and ulceration), and any clinically significant laboratory values.

- 2. Time to response in cSCC TILS. Time to response is the time from first visit until objective tumor response (CR or PR) is identified
- 3. Duration of overall response (DOR) of TILs. This will be measured from the time measurement criteria are met for CR or PR (whichever status is recorded first) until the first date that recurrence or progressive disease (PD) is objectively documented, taking as reference for PD the smallest measurements recorded since the treatment started. If no recurrence or PD is documented after PR or CR is observed the time measurement will be performed at Visit 8.
- 4. Durable response rate of TILs. The duration of overall response is ORR lasting continuously for > than or equal to 6 months.
- 5. Time to progression (TTP) of TILs. This will be measured from the time treatment is initiated until the first date that recurrence or progressive disease (PD) is objectively documented, taking as reference for PD the smallest measurements recorded since the treatment started.
- 6. Overall response rate (CR+PR) of TILs assessed by imaging technique (high frequency ultrasound) and correlate it with clinical overall response rate.
- 7. Overall clinical response rate (CR+PR) of individual TILs injected with talimogene laherparepvec (not as overall subject response). Overall response rate is defined as the proportion of injected lesions which achieved complete and partial response.

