16.2 Statistical Analysis

Any patient who was treated with at least 1 dose of talimogene laherparepvec therapy will be included in safety and efficacy analysis. Descriptive statistics (mean, median, standard deviation, 25th percentile, 75th percentile, and range) will be presented for continuous variables, such as age. Frequency counts will be presented for categorical variables such as sex and race.

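### Time to response: Kaplan-Meier censoring treats subjects withdrawn for progression as still able to respond, which overstates the cumulative probability of response

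*Combined protocol and SAP*

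**What the plan says.** Section 16.1.2 defines the endpoint: "Time to response is the time from first visit until objective tumor response (CR or PR) is identified". Section 16.2.6 gives the method: "The analysis of time to response will consist of Kaplan-Meier estimates", with a median and 95% confidence interval. Its censoring rule is: "The time to response data will be censored on those who do not respond at their last follow-up". It makes no exception for progression.

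Section 16.2 fixes the analysis set: "Any patient who was treated with at least 1 dose of talimogene laherparepvec therapy will be included in safety and efficacy analysis". Subjects who progress are therefore in the analysis.

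Four other passages decide when such a subject's follow-up ends:

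- Table 7 (Section 9.4.1.2) withdraws an injected lesion and moves it to alternative therapy "If IL-PD confirmed in two consecutive visits", or at Visit 6. For the number of injected lesions it adds: "If subject has only one, subject will be" withdrawn. A subject with further injected lesions continues.
- Section 11.4 lists as an individual stopping criterion: "75% or greater number of TILs meeting criteria for withdrawal".
- Section 9.6 gives a subject who stops treatment early one termination visit within 30 days, with lesions measured.
- Section 9.4.1.1 attaches confirmation at Visit 6 to its definition of progression and does not mention two consecutive visits.

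No section treats progression as a competing event, keeps progressors at risk to the end of follow-up, or limits the time-to-response analysis to responders.

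**The concern.** Kaplan-Meier is valid here only if a censored subject has the same future chance of responding as those still under observation. A subject withdrawn for confirmed progression does not: the lesion has grown and alternative treatment follows. Under Appendix B, best overall response counts only up to progression, so a later response would not be credited. Progression with withdrawal therefore competes with response.

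When these subjects are dropped from the risk set, each later response is divided by too small a denominator. The curve rises above the proportion of subjects who actually respond. At stake is a secondary descriptive result: a reader could see a cumulative response probability well above the response rate in the same subjects, or a median time to response in a trial where fewer than half responded.

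**Working it through.** **The plan's own figure.** The documents give no figure for time to response. The nearest is the Simon design in Section 16.2.1. With X1 ~ Bin(7, p) and X2 ~ Bin(13, p), P(X1 ≥ 5 and X1 + X2 ≥ 14) is 0.0417 at p = 0.5 and 0.8122 at p = 0.8. This agrees with the stated one-sided 0.05 and 80%. It uses a count of responders and does not pass through the Kaplan-Meier estimate.

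**Visit grid (Table 1), weeks from Visit 1.** Visit 2: 3. Visit 3: 3 + 2 = 5. Visit 4: 5 + 2 = 7. Visit 5: 7 + 4 = 11. Visit 6: 11 + 4 = 15. Visit 7: 15 + 6 = 21. Visit 8: 21 + 14 = 35.

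**Estimators.** With d responses among n at risk at each visit:

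- As planned: 1 − KM = 1 − ∏(1 − d/n), where progression withdrawals leave the risk set without counting as events.
- Competing risks: F = Σ S₋ · d/n, where S₋ is the probability of neither response nor progression withdrawal before that visit. With no other early censoring, F equals responders divided by 20.

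**Assumptions.** There are 20 subjects. The documents give no rate or timing of progression withdrawal, so both are assumed:

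- One or two withdrawals: at week 7.
- Three: one at week 5 and two at week 7.
- Four: two at week 5 and two at week 7.
- Everyone else without a response is followed to week 35.

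**One case in full.** There are 14 responders (1, 2, 3, 4 and 4 at weeks 3, 5, 7, 11 and 15) and four withdrawals.

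- Weeks 3 and 5: 19/20 × 17/19 = 17/20. Two then leave, so 15 are at risk.
- Week 7: 12/15. Two leave, so 10 are at risk.
- Week 11: 6/10. Week 15: 2/6.
- S = 17/20 × 12/15 × 6/10 × 2/6 = 0.136, so 1 − KM = 0.864 against F = 14/20 = 0.70.

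**Range.** Final value of 1 − KM by number of early withdrawals:

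| Responders | F | 1 | 2 | 3 | 4 |
|---|---|---|---|---|---|
| 10/20 | 0.50 | 0.522 | 0.547 | 0.578 | 0.613 |
| 14/20 | 0.70 | 0.731 | 0.767 | 0.812 | 0.864 |
| 16/20 | 0.80 | 0.836 | 0.880 | 0.935 | 1.00 |

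Responses were placed at weeks 5, 7, 11, 15 (1, 2, 3, 4) for the 10-responder row and at weeks 3, 5, 7, 11, 15 (1, 3, 4, 4, 4) for the 16-responder row. The excess is 2.2 to 3.6 points with one withdrawal and 11.3 to 20 points with four. The 1.00 is a boundary case in which nobody is left without an event. If four withdrawals fall at week 15 instead, both estimators give the same value in every row.

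**Effect of the termination visit.** Suppose it falls near day 30 and counts as last follow-up. Withdrawals at week 5 then stay at risk at week 7, and those at week 7 stay at risk at week 11. With four withdrawals:

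- 14 responders: S = 14/20 × 8/12 × 2/6 = 0.156, so 1 − KM is 0.844 instead of 0.864.
- 10 responders: S = 17/20 × 12/15 × 6/10 = 0.408, so 1 − KM is 0.592 instead of 0.613.

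**Median.** In the table, both methods give the same median visit in each row (week 15 for 10 responders, week 11 for 14 and 16). The exception appears just below 50%. Take 9 responders (1, 2, 2, 4 at weeks 5, 7, 11, 15) and three withdrawals. S = 19/20 × 16/18 × 12/14 × 8/12 = 0.483, so 1 − KM = 0.517 with a median of 15 weeks, while F = 0.45 and the median is not reached. Under the late termination visit, S = 17/20 × 14/16 × 8/12 = 0.496, and the 15-week median is still reported.

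**Simulation.** This used 1,500 runs per scenario with 20 subjects each, no stage 1 stop, and withdrawals at weeks 5, 7 or 11. Mean 1 − KM against mean F:

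| True response | 5% withdrawn | 10% withdrawn | 20% withdrawn |
|---|---|---|---|
| 0.50 | 0.521 / 0.504 | 0.538 / 0.503 | 0.585 / 0.500 |
| 0.65 | 0.675 / 0.651 | 0.702 / 0.649 | 0.782 / 0.654 |
| 0.80 | 0.835 / 0.801 | 0.881 / 0.799 | 0.998 / 0.799 |

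The typical median was the same visit under both methods. At 0.50 with 20% withdrawn, the median was not reached in 27% of runs under Kaplan-Meier and 41% under cumulative incidence. With all withdrawals at week 15 the difference was zero throughout.

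**The case against.** The strongest reply is that early progression withdrawal may be rare. Section 9.4.1.1 ties progression to a Visit 6 assessment. If withdrawal waits for that visit and responses are dated by then, the bias vanishes. Subjects with several injected lesions stay on when one progresses, unless the 75% criterion in Section 11.4 is met. Withdrawal by Visit 3 is an inference: it needs progression at Visit 2, after one injection, and again at Visit 3. All this stands as a limit on size, but Table 7 does allow withdrawal before Visit 6, and Section 16.2.6 does not provide for it.

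The termination visit in Section 9.6 also moves the censoring date later. That stands, and takes about 2 points off the four-withdrawal cases above.

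A case with fewer than half responding should be uncommon at full sample size. At a true rate of 45%, the chance of at least 5 responses in the first 7 is about 0.117 + 0.032 + 0.004 = 0.153.

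Two stronger readings are tempting. A reader might infer that the analysis contradicts the primary response rate. It does not: that rate is a proportion judged by the Simon rule, and time to response carries no test or decision. A reader might also infer that response will generally look faster. The curve does rise too steeply, but on this visit grid the median seldom moves.

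**Conclusion.** The point holds for the cumulative probability of response. Applied as written, Section 16.2.6 gives a curve that is never below the cumulative incidence and lies above it whenever a progression withdrawal precedes a later response. The likely size runs from nothing to a few points if early withdrawals are few, and reaches about 11 to 20 points with four in 20, or somewhat less if the termination visit comes late and counts as last follow-up. These figures rest on assumed numbers and dates of withdrawal. That progressors are censored is inferred by reading Sections 16.2, 16.2.6, 9.4.1.2, 9.6 and 11.4 together; no single sentence says it. The effect on the median matters mainly when response is near 50%. The endpoint is secondary and descriptive. The correction is worth making because any error runs in the favourable direction and the remedy is cheap.

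**What to change.** In Section 16.2.6, replace Kaplan-Meier with the cumulative incidence of response (Aalen-Johansen). Name as competing events progression leading to withdrawal, start of alternative treatment, and death, each before response. Keep only administrative loss and withdrawal of consent as censoring. Report the median time among responders as well, labelled as such.

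State which response definition dates the event. The curve will agree closely with the proportion of subjects ever responding. It equals the primary response rate only if the same Visit 6 confirmation (Section 9.4.1.1) is required and nobody is otherwise censored early; Section 16.1.2 does not require that confirmation for time to response.

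Reconcile Section 9.4.1.1 (Visit 6) with Table 7 (two consecutive visits or Visit 6) on when progression is confirmed, because this sets the event date.

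The cost is a change of wording and one standard routine, with no further data or subjects. The downside is a slightly less favourable curve.

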16.2.7 Overall response rate (CR+PR) in TNILs

For each group, we will use a Simon two-stage optimum design to test that the proportion with ORR is \geq 80% (alternative hypothesis) versus ORR \leq 50% (null hypothesis).

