1.4 Patient Population

The patient population for this study will be non-immunocompromised patients presenting with at least one eligible cSCC. The TILs should be located in anatomical sites other than head and neck.

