2.3 Number of subjects

There will be approximately 20 subjects participating in this protocol.

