3.2 Secondary Objective

- To assess the safety and adverse effect profile of talimogene laherparepvec in low risk cSCC. This will be determined by incidence of all adverse events (AEs), grade ≥ 3 AEs, safety adverse events (SAEs), and events requiring the discontinuation of study drug, local effects on the tumor (ie, pain, inflammation and ulceration), and any clinically significant laboratory values.
- 2. To determine the time of response in cSCC TILs. This will be measured from the time from the first visit until objective tumor response (CR or PR) is identified.
- 3. To measure the duration of overall response (DOR) of TILs. This will be measured from the time measurement criteria are met for CR or PR (whichever status is recorded first) until the first date that recurrence or progressive disease (PD) is objectively documented, taking as reference for PD the smallest measurements recorded since the treatment started. If no recurrence or PD is documented after PR or CR is observed the time measurement will be performed at Visit 8.
- 4. To measure the durable response rate (DRR) of TILs. The duration of overall response is ORR lasting continuously for > than or equal to 6 months.

- To measure the time to progression (TTP) of TILs. This will be measured from the time treatment is initiated until the first date that recurrence or progressive disease (PD) is objectively documented, taking as reference for PD the smallest measurements recorded since the treatment started.
- 6. To measure the overall response rate (CR+PR) of TILs by high frequency ultrasound and correlate it with clinical overall response rate.
- 7. Overall clinical response rate (CR+PR) of individual TILs injected with talimogene laherparepvec (not as overall subject response).
- 8. To determine the overall clinical response rate (CR+PR) observed in TNILs that are present in the treated anatomical location (if applicable).

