- 8. Overall clinical response rate (CR+PR) in cSCC TNILs. Overall response rate is defined as the proportion of subjects who achieved complete and partial response in TNILs. cSCC TNILs will be categorized by distance to TILs. Group 1: < 5 cm, Group 2: 5 to 15 cm, Group 3: >15 cm. Response rates in TNILs will be measured using a ruler or calipers. Digital photograph of the lesion will be recorded each visit. Complete response of TNILs will be defined as the disappearance of all TNILs and partial response defined as at least a 30% decrease in the sum of the diameters of TNILs, taking as reference the baseline sum diameters. Progression is defined as 20% increase of at least 5 mm in the sum of the longest diameters of the TNILs compared with the smallest sum of the longest diameter burden). Stable disease (SD) is defined as decrease in tumor size <30% or an increase in size <20% that is less than 5 mm in the sum of the longest diameters of the TNILs compared with the smallest sum of the longest diameters of the TNILs compared with the smallest sum of the longest diameters of the TNILs compared with the smallest sum of the longest diameters of the TNILs compared with the smallest sum of the longest diameters of the TNILs compared with the smallest sum of the longest diameters of the TNILs compared with the smallest sum of the longest diameters of the TNILs compared with the smallest sum of the longest diameters of the TNILs compared with the smallest sum of the longest diameters of the TNILs compared with the smallest sum of the longest diameters of the TNILs compared with the smallest sum of the longest diameters of the TNILs compared with the smallest sum of the longest diameters of the TNILs compared with the smallest sum of the longest diameters of the TNILs compared with the smallest sum of the longest diameter recorded.

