16.2.1 Overall Response Rate (ORR)

The analysis of ORR will use a Simon two-stage optimum design to test that the proportion with ORR is \geq 80% (alternative hypothesis) versus ORR \leq 50% (null hypothesis). In the first stage, 7 patients will be recruited. If \leq 4 have ORR the trial will be terminated. If 5 or more have ORR, accrual will continue to the second stage. In the second stage, an additional 13 patients will be recruited. At the end of the second stage, if \geq 14 patients have ORR then TVEC will be considered promising for further study. This design yields 80% statistical power with a one-sided alpha level of 0.05.

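### The TNIL test in section 16.2.7 has no stage sizes, cut-offs, alpha or power, and at the primary design's error rates needs 17 to 20 TNIL-bearing subjects in each of three distance groups

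*Combined protocol and SAP*

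**What the plan says.** Section 16.2.7 is one sentence: "For each group, we will use a Simon two-stage optimum design to test that the proportion with ORR is" 80% or more (alternative) against 50% or less (null). It goes no further.

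The groups come from section 16.1.2, item 8, which sorts TNILs by distance to TILs: "Group 1: < 5 cm, Group 2: 5 to 15 cm, Group 3: >15 cm". The same item makes the subject the unit of analysis: "Overall response rate is defined as the proportion of subjects who achieved complete and partial response in TNILs". It bases response on the sum of diameters of all of a subject's TNILs.

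Design parameters appear only in section 16.2.1, for the primary TIL endpoint: 7 subjects at stage 1, stop at 4 or fewer responders, then "In the second stage, an additional 13 patients will be recruited", with success at 14 or more. That section adds: "This design yields 80% statistical power with a one-sided alpha level of 0.05".

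On numbers, section 2.3 says "There will be approximately 20 subjects participating in this protocol". Section 1.4 defines the population as "non-immunocompromised patients presenting with at least one eligible cSCC" and does not mention TNILs. Section 3.2, item 8, treats the TNIL objective as one to be assessed only where it applies. Table 1 (section 2.4) allows up to 10 TNILs per subject, with no more than 2 in the same anatomical area as a TIL. Section 16.3 describes a single interim look at 7 recruited subjects and does not mention TNILs.

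**The concern.** A two-stage test is defined by its stage sizes and cut-offs, and section 16.2.7 supplies neither. Borrowing them from section 16.2.1 would settle the cut-offs, but the trial has too few subjects to fill the groups. A two-stage rule also exists to stop or continue accrual, and here accrual follows the TIL result alone, so the TNIL rule governs nothing.

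A response beyond the injected lesion is part of the hypothesis in section 4.1. A distance group that does not reject because few subjects have such lesions could be reported as evidence against that effect. If cut-offs are chosen once the group sizes are known, the choice depends on the data.

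**Working it through.** **Inputs.** Null rate p0 = 0.50 and alternative p1 = 0.80 (16.2.7). Stage 1: n1 = 7, stop at 4 or fewer. Stage 2: 13 more, success at 14 or more of 20. One-sided alpha 0.05, power 80% (all 16.2.1). Three groups, analysed by subject (16.1.2, item 8). About 20 subjects in total (2.3).

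**Step 1: reproduce the primary design.** P(success) = sum over x = 5, 6, 7 of P(X1 = x) × P(X2 ≥ 14 − x), with X1 ~ Bin(7, p) and X2 ~ Bin(13, p).

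- p = 0.8: 0.2753 × 0.9009 + 0.3670 × 0.9700 + 0.2097 × 0.9930 = 0.812.
- p = 0.5: 0.1641 × 0.1334 + 0.0547 × 0.2905 + 0.0078 × 0.5000 = 0.042.

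The stated 80% power and alpha of 0.05 are reproduced. An exhaustive search confirms 4/7, 13/20 as the Simon optimal design (expected size under the null 9.9).

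**Step 2: smallest design with these hypotheses and error rates.**

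- Two-stage minimax: 10/15, 11/17 (alpha 0.0488, power 0.828). No two-stage design has a maximum below 17.
- Smallest single-stage exact test: n = 18, success at 13 or more (alpha 0.0481, power 0.867).

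Each band therefore needs about 17 to 20 subjects with a TNIL in it. One subject may count in several bands. Even so, filling all three would need nearly every subject in the trial to have a TNIL in each band. A subject whose TNILs all lie in one treated area has at most 2 of them there, so fills at most two bands.

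**Step 3: what happens with n subjects in a band at a true rate of 80%.** The documents do not give n, so two readings are shown over a range.

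*Reading A: the rule of 16.2.1 carried over unchanged (stop at ≤ 4 of 7, success at ≥ 14).* The formula of step 1 with X2 ~ Bin(n − 7, 0.8):

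| n | ≤ 13 | 14 | 15 | 16 | 17 | 18 | 19 | 20 |
|---|---|---|---|---|---|---|---|---|
| Power | 0% | 4% | 17% | 35% | 54% | 68% | 76% | 81% |

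On this reading 13 responders out of 13 (one-sided p = 0.5^13 = 0.0001; exact 95% CI 75% to 100%) would still miss the cut-off.

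*Reading B: a single-stage exact cut-off, one-sided 0.05, set for the n attained.* The cut-off is the smallest r with P(Bin(n, 0.5) ≥ r) ≤ 0.05; power is P(Bin(n, 0.8) ≥ r):

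| n | Cut-off r | Alpha | Power |
|---|---|---|---|
| 4 | none (0.5^4 = 0.0625) | – | 0% |
| 5 | 5 | 0.031 | 33% |
| 8 | 7 | 0.035 | 50% |
| 10 | 9 | 0.011 | 38% |
| 13 | 10 | 0.046 | 75% |
| 16 | 12 | 0.038 | 80% (0.798) |

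Power does not rise steadily with n because the attainable alpha is discrete.

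**Step 4: group membership.** Table 1 requires TILs in the same area to be 10 cm apart. One TNIL can then lie less than 5 cm from one TIL and 5 to 15 cm from another, and section 16.1.2 does not say which distance counts. Section 16.1.2 and Appendix B sum all of a subject's TNILs, so a subject with TNILs in two bands has one response and no defined response per band. No listed study procedure records the distance from TIL to TNIL.

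**The case against.** The strongest reply is that section 16.2.7 never says the cut-off of 14 carries over, nor that a short group counts as failed. This stands. A reader might infer that any band of 13 or fewer must fail, but that is Reading A only; under Reading B a band of 13 rejects at 10 responders with 75% power. A reader might also infer that 80% power needs all 20 subjects in a band. That holds only if the stage-1 stop is applied; without it, a cut-off of 14 gives 84% power at n = 19. Nor are 60 different subjects needed, because one subject can enter several bands.

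The second reply is that little depends on this endpoint. It is the last of eight secondary endpoints, and in the Appendix B table TNIL status does not alter overall response. No stopping or success decision uses it. This also stands, and limits the point to how the TNIL result can be interpreted.

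The third reply is that stating exact cut-offs for each n, or labelling the tests exploratory, would be enough. That would supply the missing specification. It would not make a non-significant result in a small band informative, as the power under Reading B shows.

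**Conclusion.** The concern holds in a conditional form. That the TNIL test lacks stage sizes, cut-offs, alpha and power is true on any reading. That each band needs about 17 to 20 TNIL-bearing subjects rests on one assumption, that the error rates of section 16.2.1 apply. Given that, the trial can hardly be expected to deliver the test in all three bands. How badly a given band falls short cannot be fixed from the documents, because TNIL prevalence is not stated; the two tables above give the range. A reader might infer that the trial's main conclusion is at risk. The documents do not support that: the primary TIL decision uses its own, correctly specified design.

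**What to change.** Replace the test in section 16.2.7 with estimation, and state that no hypothesis test or two-stage rule applies to TNILs.

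- Report the subject-level TNIL response rate among subjects with at least one TNIL, with an exact 95% confidence interval.
- Report response by distance band descriptively. Either define a subject's response within a band on the sum of diameters of that subject's TNILs in that band, or report by lesion with an interval that allows for clustering within subject.
- State which TIL the distance is measured to, for example the nearest. Record that distance at baseline or derive it from the regional photographs.

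**Cost.** A wording amendment to section 16 with IRB approval (section 18.2), and possibly one recorded distance per TNIL. The formal TNIL test is given up. Intervals in small groups will be wide: exact 95% limits are 44% to 97% for 8 of 10 and 28% to 99% for 4 of 5.
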